4.2 Primary Outcome

The primary outcome is adherence to prescribed oral targeted therapy across the 12-week trial period. Adherence is defined by the overall proportion of adherent days and classified dichotomously as adherent if total proportion of days is $\geq 95\%$. Longitudinal adherence outcomes for all participants will be captured using microelectronic monitoring system (MEMS) caps, surveys, and electronic medical record (EMR) data.

4.3 Secondary Outcome

The secondary outcome is persistence defined as the number of consecutive days on the prescribed medication regimen and conversely gaps in overall treatment.

4.4 Exploratory Outcomes

Exploratory patient-reported outcomes including health-related quality of life (HRQOL), symptom burden, patient satisfaction, financial toxicity, social and behavioral determinants of health (SBDH), medication self-efficacy, health literacy, and healthcare utilization will be evaluated using validated survey measures.

5. STUDY DESIGN

5.1 Overview

We will evaluate the effect of a bidirectional conversational agent (“Penny”), compared to usual care, on patient adherence to oral targeted therapies using a two-arm randomized-controlled trial (Aim 1), and explore how multilevel factors impact the effectiveness and implementation of the strategy by collecting qualitative and quantitative data from clinicians and patients (Aim 2). The intervention will leverage a third-party company, Memora Health, who have developed a HIPAA-compliant, SMS text-based platform and worked previously with Penn Medicine. Consented patients with advanced lung cancer receiving oral targeted therapies within UPHS will be randomized (1:1) to Penny or usual care. Longitudinal adherence outcomes for all participants will be captured using microelectronic monitoring system (MEMS) caps, surveys, and EMR data. Following active intervention, semi-structured interview data will be collected from a subsample of 30 patients and 30 clinicians to further assess mechanisms shaping adherence, and the acceptability, effectiveness, and future implementation of Penny into routine cancer care.

5.2 Study Setting

The study will be conducted at two hospitals affiliated with the University of Pennsylvania Health System: Perelman Center for Advanced Medicine/Hospital of University of Pennsylvania (PCAM) and Penn Presbyterian Medical Center (PPMC).

5.3 Study Duration

Aim 1: Study enrollment for each participant will last approximately 15-weeks including consent and post-assessment. Observation will begin no earlier than one week after therapy initiation (to allow for a brief prescription run-in period for new starts) and end either 12-weeks later or at therapy discontinuation, whichever is shorter. Post-assessment will occur within 2 weeks after each patient's active observation period. We anticipate the active trial will last approximately nine months, with anticipated enrollment beginning in November-December 2020 and ending in October 2021. Data ascertainment and analyses will continue through December 2021 or later as needed.

Aim 2: Study enrollment for each interview participant will last approximately 60-90 minutes including consent, semi-structured interview, and completion of brief written questionnaire. We anticipate that interviews will begin in December 2020 and continue through November 2021. Analyses will continue through December 2021 or later as needed.

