5.7 Participant Remuneration

In recognition of time needed to complete data collection surveys and the importance of retaining the MEMS caps, incremental remuneration will be provided to patients (\$25 at each time point) for total of \$75. All enrolled patients will be asked to complete a brief baseline survey (T0) and will receive \$25 upon completion of the baseline survey. Additionally, all patients will be re-contacted approximately 6 weeks after enrollment (T1) and after study completion (12 weeks from study start date; T2) to conduct two follow-up surveys. Patients who complete the midpoint (T1) survey will receive an additional \$25 upon survey completion. Patients will receive the final \$25 upon return of the electronic monitoring cap to the study team. If patients do not complete any additional surveys beyond baseline and do not return the electronic monitoring cap, they will not receive any additional remuneration beyond the initial \$25. Patients who do not complete the baseline survey will not be enrolled and not provided with any remuneration.

Patients will receive remuneration through issuance of GreenPhire ClinCards that will be mailed to participants within 10 days of enrollment and completion of baseline survey. These ClinCards can be used in the same manner as a credit card. ClinCards can be re-loaded remotely with additional funds by study team members after completion of study activities. Given the amount of participant remuneration, we are requesting a waiver of collection of social security numbers for the ClinCards.

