8.2 Assessment Procedures

MEMS Caps. Adherence data will be assessed via MEMS caps, which capture a date and time stamp each time the pill bottle is opened. MEMS caps are considered the gold standard of objective adherence measurement over other methods of adherence monitoring,^{31,32} and have been used successfully in previous studies of oral anticancer agents.^{5,25} MEMS data will be scanned to a secure web portal by research staff at the time of clinic appointments. All participants will receive MEMS cap(s) regardless of study assignment. Participants will be instructed to use this system for storage throughout the study, and to log any bottle openings for purposes other than pill ingestion (e.g., to check remaining supply) in a daily journal. After patients complete the baseline survey, a study team member will mail the MEMS Caps directly to the patients with instructions on how to install the MEMS cap. Patients will be contacted by phone approximately 7-10 days after the MEMS cap is mailed to them to confirm receipt and answer any questions. Patients will be instructed to begin using the MEMS cap the day immediately following the phone call as this will be their study start date.

Online Surveys. Trial participants (Aim 1) will be asked to complete online surveys at three timepoints: baseline assessment (T0) will occur at time of enrollment, followed by mid-point assessment approximately 6 weeks later (T1), and final assessment occurring within 2 weeks of trial completion (T2). Data will be captured via REDCap, a secure, web-based application for collecting and managing survey data³³. For REDCap data, patients will receive individualized links to each survey and will be contacted up to three times by email, text message, and/or phone to complete each survey. To increase data completion and study retention incremental compensation will be provided to patients. Specific measures to be assessed in the survey are described below.

Medical Record Data: Medical record data from enrolled patients will be abstracted across the study period to evaluate diagnostic and treatment changes, clinical characteristics, and healthcare utilization. We will also use medical record data to identify and recruit potentially eligible patients as outline in the HIPAA waiver.

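### The protocol does not secure a common T2 time: section 5.3 ties the final survey to the end of observation, section 5.7 to 12 weeks from study start

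*Combined protocol and SAP*

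**What the plan says.** Three sections date the final survey.

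- Section 5.3 (Study Duration): a patient's observation will "end either 12-weeks later or at therapy discontinuation, whichever is shorter". It continues: "Post-assessment will occur within 2 weeks after each patient's active observation period". The final assessment is thus dated from the individual patient's end of observation.
- Section 5.7 (Participant Remuneration): all patients are contacted again "after study completion (12 weeks from study start date; T2"). This is a fixed date, with no exception for patients who have stopped therapy.
- Section 8.2 (Assessment Procedures): "final assessment occurring within 2 weeks of trial completion (T2"). It does not say whether a patient who stops therapy early has completed the trial at that moment or only at week 12.

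The midpoint survey is counted from enrollment in both places that mention it. Section 5.7 has "all patients will be re-contacted approximately 6 weeks after enrollment (T1"), and section 8.2 has "baseline assessment (T0) will occur at time of enrollment, followed by mid-point assessment approximately 6 weeks later (T1"). No section says whether T1 is still sent once a patient's post-assessment has been done.

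Section 8.3 says that patient-reported outcomes are measured at several time points. Section 9 names no analysis time or visit window for them.

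**The concern.** For a patient who stays on therapy to the end, all the rules lead to about the same date. For a patient who stops early, section 5.3 moves the final survey forward to the stop date and section 5.7 leaves it at week 12. Nothing says which rule governs.

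This is more than a missing detail. Under section 5.3 the survey date is set by an event that occurs after randomisation and that the intervention may change. Persistence is the trial's secondary outcome, and the chatbot is meant to work partly through better symptom management. If the arms differ in when patients stop, they would also differ in when patients are surveyed, and randomisation does not protect against that. T2 would pool scores taken soon after stopping therapy with scores taken at weeks 12 to 14. A difference between arms in quality of life, symptom burden, satisfaction or self-efficacy could then partly reflect survey timing. The mediation analyses in section 9.2 would inherit the problem wherever self-efficacy or symptom measures come from these surveys.

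**Working it through.** **Inputs**

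- Observation lasts 84 days, or until therapy stops if sooner; the post-assessment follows within 14 days (5.3).
- T2 is 12 weeks after study start (5.7).
- T1 is about 42 days after enrollment (5.7, 8.2).
- The phone call comes 7 to 10 days after the cap is mailed, and study start is the next day (8.2). Study start is therefore 8 to 11 days after mailing.
- Assumptions: the cap is mailed on the day of enrollment, and observation begins on the study start date.
- Section 5.3 speaks of a post-assessment rather than T2. I treat them as the same event, because section 8.2 gives T2 a two-week window too and T2 is the only survey after T1.

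**1. Reproduce the plan's own figure.** Section 5.3 gives about 15 weeks per participant.

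- (8 + 84 + 14) / 7 = 15.1 weeks
- (11 + 84 + 14) / 7 = 15.6 weeks

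The figure holds for a patient who completes 12 weeks, so the inputs are read correctly.

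**2. T2 under each rule.** For a stop at study week d, section 5.3 puts T2 between week d and week d + 2, and section 5.7 puts it at week 12. The gap runs from 10 − d to 12 − d weeks.

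| Stop (study week) | T2 under 5.3 (study weeks) | T2 under 5.7 | Gap (weeks) |
|---|---|---|---|
| 2 | 2–4 | 12 | 8–10 |
| 3 | 3–5 | 12 | 7–9 |
| 4 | 4–6 | 12 | 6–8 |
| 8 | 8–10 | 12 | 2–4 |
| 10 | 10–12 | 12 | 0–2 |

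From about week 10 the section 5.3 window reaches week 12 and both rules can be met. Before that they cannot.

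**3. Order of T1 and T2.** In weeks from study start, T1 falls at (42 − 11) / 7 = 4.4 to (42 − 8) / 7 = 4.9. Under section 5.3:

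- The whole T2 window closes before T1 if d + 2 is below 4.4 to 4.9, that is, for a stop before about week 2.4 to 2.9.
- The window spans T1 for stops from then until about week 4.4 to 4.9.
- For later stops T2 follows T1.

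Under section 5.7, T2 is always 12 − 4.9 = 7.1 to 12 − 4.4 = 7.6 weeks after T1, and the order cannot reverse.

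**4. Number affected.** The documents give no discontinuation rate and no distribution of stop times, so this cannot be computed.

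**The case against.** The strongest reply is that section 5.7 already supplies a common date for all patients. A reader might infer that patient-reported outcomes *will* be compared at different times. The documents do not support that: it follows only if section 5.3 is the rule applied. This stands, and the supportable claim is that a common time is not secured.

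A reader might also infer that the final survey will come before the midpoint survey. That needs section 5.3 to govern, a stop before about study week 5, and T1 still being sent after the post-assessment. No section settles the last condition.

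A third tempting reading is that T1 is badly misplaced because it is counted from enrollment. Under section 5.7, T2 falls 92 to 95 days after enrollment (84 + 8 to 84 + 11), so day 42 is 44 to 46% of the way through the survey series (42/95 to 42/92). The offset is the same in both arms and creates no difference between them.

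It is also fair to say that the outcomes are exploratory, that this is a single-center pilot in which one team runs the surveys, and that surveying near the end of exposure suits instruments tied to current use, such as medication self-efficacy and chatbot usability. These points limit the severity and describe a real cost of the fix. They do not remove the conflict, because the protocol neither chooses end-of-exposure timing openly nor plans an analysis for unequal survey times.

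**Conclusion.** The concern holds in a limited form. Sections 5.3 and 5.7 give different T2 dates for patients who stop therapy before about study week 10, and section 8.2 does not resolve them. For an individual patient the difference reaches 8 to 10 weeks for a stop at week 2 and shrinks to 0 to 2 weeks at week 10.

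If section 5.3 is followed, survey timing depends on a post-randomisation event that may differ by arm. The exploratory patient-reported comparisons and the survey-based mediator analyses can then be biased. The direction and size of that bias cannot be stated, because the documents report neither how many patients stop nor why they stop. The MEMS primary endpoint and the sample size are unaffected.

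The T1 ordering result also rests on same-day mailing of the cap; later mailing would bring T1 earlier relative to study start. The point should be corrected, but it does not threaten the main conclusion of the trial.

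**What to change.** Reconcile sections 5.3, 5.7 and 8.2 on one rule for both arms:

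- T2 at 12 weeks from the study start date, with a window of +14 days, completed whether or not therapy has been discontinued. This adopts the date already in section 5.7.
- T1 kept on its schedule after discontinuation.
- Discontinuation status recorded at each survey.

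Moving T1 to study day 42 would be tidier but is optional.

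The change needs wording in three sections and a new REDCap schedule. It adds no survey or payment. There are two real downsides. Some patients who have stopped therapy will not answer a later survey; section 5.7 ties the last $25 to return of the cap rather than to T2, so a patient who returns the cap on stopping has no payment left to prompt a reply. Items about current drug or chatbot use will also be answered longer after stopping, about nine weeks later for a stop at week 3 (12 − 3). The recorded discontinuation status lets the analysis describe both. The rule should be settled before more surveys are sent, since a T2 taken at the wrong time cannot be retaken.

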5.4 Target Population

Aim 1. The study aims to enroll 170 adult patients (18 years or older) with advanced NSCLC who have initiated oral targeted therapies at UPHS. These include afatinib, erlotinib, dacomitinib, gefitinib and osimertinib for patients harboring sensitizing EGFR mutations; and alectinib, brigatinib,, crizotinib, and lorlatinib for patients with anaplastic lymphoma kinase (ALK) or ROS1 rearrangements. To be eligible, participants must be receiving ongoing cancer care at a participating site; have access to a mobile phone with SMS text messaging capabilities; be able to read and respond to questions in English; and must have started taking oral targeted therapies no earlier than January 1, 2020 and no later than the end of study recruitment (estimated October 2021).

Aim 2. The study aims to interview 30-45 patients and 15-30 clinicians. Patients will be eligible if they are enrolled in the intervention trial (Aim 1). Clinicians will be eligible if they actively provide care for cancer patients on targeted oral therapies at one of the study sites (including but not limited to oncologists, advanced practice providers, triage nurses, and pharmacists).

5.5 Sample Size and Accrual

Aim 1. The study sample will be drawn from adults seeking cancer care at the University of Pennsylvania's Abramson Cancer Center (ACC). Across recruitment sites, approximately 215 patients with lung cancer had orders for one of the included oral targeted therapies from January-September 2020. For this study, we will include both patients who have new prescriptions (after study launch) and patients previously taking these medications in 2020 (and who continue to take these medications at the time of eligibility assessment). Based on preliminary studies with Penny, we conservatively estimate that $\geq 40\%$ of patients approached will be eligible and consent to participate in this study. Of the 215 patients who started taking these medications in 2020 and estimated number of new starts during the study enrollment period (estimated 25 new starts per month), we anticipate that we will reach our target sample size of 170 in approximately 9-12 months (enrolling an estimated 85 patients who are currently taking these medications and 10 patients monthly who are new medication starts across the enrollment period). Allowing for a 15% loss to follow up, 72 participants will remain in each arm ($n=144$). Our full sample will provide 80% power to detect minimum effect of 20.9% or greater between the intervention and control group (assuming previously observed 65.5% adherence rate in controls and using fisher's exact test⁷), an effect size that is clinically significant and appropriate for this pilot stage of research.

Aim 2. *Patients* will be eligible if they are enrolled in the intervention trial, and purposively sampled by race, age, drug type, study arm, and adherence outcome to participate in the interview (in batches of 15) to increase variation of perspectives.²⁷ Recruitment will continue until we reach our target sample of 30-45 patients. This number is based on the estimated sample needed to reach data saturation on exploratory themes; however, interviews will continue until data saturation is achieved. *Clinicians* will be eligible if they actively provide care for cancer patients on targeted oral therapies at one of the study sites (including but not limited to oncologists, advanced practice providers, triage nurses, and pharmacists). As with the patient sample, our target of 15-30 clinicians is based on the estimated sample needed to reach qualitative data saturation on exploratory themes, but interviews will continue until data saturation is achieved.

5.6 Key Inclusion and Exclusion Criteria

Aim 1: Trial Participants

Inclusion Criteria

- Adult patient (age > 18 years) with advanced NSCLC at UPHS who is receiving one of the following nine oral therapies: afatinib, erlotinib, dacomitinib, gefitinib, osimertinib, alectinib, brigatinib, crizotinib, or lorlatinib.
- Patient possession of a mobile device that can send/receive SMS texts
- Ability to respond to questions and engage with “Penny” in English
- Ability to provide informed consent to participate in the study
- Blanket approval from the patient’s medical oncology to be approached

Exclusion Criteria

- Inability to respond to questions and engage with “Penny” in English
- Inability or unwillingness to provide informed consent to participate in the study
- Inability to engage with SMS text-messaging platform
- Concurrent enrollment in a therapeutic clinical trial
- Lack of blanket approval from the patient’s oncologist

Aim 2: Interview Participants: Patients

Inclusion Criteria

- Adult patient who consented and enrolled in the intervention trial (Aim 1)
- Ability to respond to interview questions in English
- Ability to provide informed consent to participate in the study

Exclusion Criteria

- Did not meet eligibility criteria to enroll in the intervention trial (Aim 1)
- Inability to respond to interview questions in English
- Inability to provide informed consent to participate in the study

Aim 2: Interview Participants: Clinicians

Inclusion Criteria

- Clinician employed by UPHS who routinely provides care for cancer patients on targeted oral therapies at one of the recruiting study sites including but not limited to oncologists, advanced practice providers, triage nurses, and pharmacists.
- Ability to respond to interview questions in English
- Ability to provide informed consent to participate in the study

Exclusion Criteria

- Does not provide routine care for cancer patients on oral targeted therapies at UPHS
- Inability to respond to interview questions in English
- Inability to provide informed consent to participate in the study

5.7 Participant Remuneration

In recognition of time needed to complete data collection surveys and the importance of retaining the MEMS caps, incremental remuneration will be provided to patients (\$25 at each time point) for total of \$75. All enrolled patients will be asked to complete a brief baseline survey (T0) and will receive \$25 upon completion of the baseline survey. Additionally, all patients will be re-contacted approximately 6 weeks after enrollment (T1) and after study completion (12 weeks from study start date; T2) to conduct two follow-up surveys. Patients who complete the midpoint (T1) survey will receive an additional \$25 upon survey completion. Patients will receive the final \$25 upon return of the electronic monitoring cap to the study team. If patients do not complete any additional surveys beyond baseline and do not return the electronic monitoring cap, they will not receive any additional remuneration beyond the initial \$25. Patients who do not complete the baseline survey will not be enrolled and not provided with any remuneration.

Patients will receive remuneration through issuance of GreenPhire ClinCards that will be mailed to participants within 10 days of enrollment and completion of baseline survey. These ClinCards can be used in the same manner as a credit card. ClinCards can be re-loaded remotely with additional funds by study team members after completion of study activities. Given the amount of participant remuneration, we are requesting a waiver of collection of social security numbers for the ClinCards.

6. RANDOMIZATION

6.1 Groups

Arm 1: Intervention Group

The intervention is an automated, text-messaging program (chatbot) named “Penny” that is guided by artificial intelligence and natural language process. Penny engages patients in real time via text messaging and continues to learn from interactions. Patients can also directly communicate with Penny at any time. Core functionalities include: (1) real-time dosing instructions, (2) motivational reminders, and (3) symptom monitoring with self-management support. Penny transmits data from text interactions into the secure online dashboard in real time, allowing for enhanced communication and longitudinal monitoring between clinicians and patients. Penny is essentially a virtual care team member, always available to support patients receiving complex oral anticancer therapies. Preliminary data from 10 cancer patients indicate that Penny helped patients to manage side effects and adherence, and can be integrated into care safely and effectively.²⁸ This project will expand upon these findings to evaluate the efficacy of Penny as a patient-directed intervention, and to explore how multilevel mechanisms may impact its acceptability and effectiveness in routine care.

Over an approximate 12-week treatment period, Penny will guide patients randomized to the treatment arm through when and how to take their oral therapies. Penny will additionally monitor patient-reported side effects based on the PRO version of Common Terminology Criteria for Adverse Events (PRO-CTCAE) grading and established clinical pathways used currently at Abramson Cancer Center to escalate and manage patient-reported symptoms (See Appendices).^{29,30} If the side effect is determined to be Grade 1-2 (mild to moderate), patients will be walked through self-care by the chatbot utilizing clinically approved and pre-determined symptom management pathways. If the side effect is deemed Grade 3 (severe) or higher or if the chatbot does not recognize the symptom to triage, the patient will be advised to call his/her care team and a real-time escalation message will be sent to the clinical

research team's inbox to follow-up directly with the patient. While the chatbot will be responding independently based on embedded algorithms, clinical research team members will monitor and audit conversations daily between the patient and Penny to validate its safety, track for any information that may be relayed to the patient incorrectly and intervene upon these events to guarantee patient safety. Clinical research team members include [name] (Physician, Medical Oncology), [name] (Nurse Practitioner, Medical Oncology), [name] (Clinical Pharmacy Specialist, Thoracic Oncology), and [name] (Outpatient Clinical Oncology Pharmacy Specialist). Additionally, any Grade 3-4 toxicities or side effects that are severe will be triaged directly to the patient's care team. Coding corrections that are not related to symptom monitoring (e.g. inability to recognize new words or commands from patients) will also be reviewed in real-time within the chatbot by Memora Health team members to improve the quality of communication. All issues will be tracked and any adverse events or deviations from protocol will be reported to the IRB as outlined below. To provide additional safety, the research team will communicate clearly (in writing and verbally at several time points) that the intervention is experimental, and that patients should always reach out to their care team directly if they are uncertain or if they are facing an emergency.

Arm 2: Usual Care

Patients in the usual care arm will receive standard of care for symptom monitoring and management of side effects for patients with cancer at Abramson Cancer Center. This includes patient education at the time of prescribing and guidance to call providers or triage nurses if anything issues or questions arises between scheduled appointments.

